12. ADVERSE EVENTS: DEFINITIONS AND MANAGEMENT

At the time of written informed consent, the subject must be given the name and telephone number of personnel at the study site who can be contacted in the event of an emergency or to report any medical symptom or untoward medical occurrence that is of concern to the subject. Investigators will closely monitor the subject for adverse events.

All adverse events reported by the subject or observed by study site personnel from time of informed consent until completion of the study or premature withdrawal must be recorded in the subject's CRF as per the CRF instructions. Adverse events are to be recorded regardless of relationship to study drug. Information to be recorded will include, but not be limited to, relationship of the event to study drug and severity of the event. These terms are defined in Sections 12.4.5.5 &12.4.5.6 below. Specific instructions for management of adverse events will be reviewed with study site personnel by the Clinical Monitor prior to study start.

12.1 Definitions

12.1.1 Pre-Dosing Signs and Symptoms

For the purposes of this study, any sign (including a clinically significant laboratory result) or medical diagnosis noted by medical personnel, or symptom reported by the subject that occurs from the time the subject signs the informed consent to the start of study drug treatment is considered to be *preexisting* and should not be reported as an adverse event unless it worsens subsequent to the start of study drug treatment.

12.1.2 Adverse Events

For the purposes of this study, any sign (including a clinically significant laboratory result) or medical diagnosis noted by medical personnel, or symptom reported by the subject, regardless of relationship to investigational drug, that is treatment-emergent is considered to be an adverse event.

TaiwanJ Pharmaceuticals defines treatment-emergent are defined as follows:

- 1) Has onset any time after the start of investigational drug treatment OR
- 2) Has worsened since the event was previously reported (this includes worsening of signs, symptoms, abnormal laboratory values, or diagnoses that were present prior to the first dose of investigational drug but then worsened any time after the start of investigational drug treatment)

12.1.3 Classification of Events as Serious

As soon as a subject has given written informed consent to participate in the study, any abnormal sign (including the clinical manifestations of an abnormal laboratory result) or medical diagnosis noted by medical personnel, or symptom reported by the subject regardless of whether or not the subject has received investigational drug is to be classified by the investigator as either a serious or non-serious event using the following definition:

Events are classified as serious if they meet any of the following criteria (in accordance with 21 United States Code of Federal Regulations Part 312.32 and the recommendations of the International Conference on Harmonization (ICH) [Federal Register, October 7, 1997, Vol 62, No. 194, pp 52239-45]):

- Any death
- Any life-threatening event, i.e., an event that places the subject, in the view of the investigator, at immediate risk of death from the event as it occurred (does not include an event that, had it occurred in a more severe form, might have caused death)
- Any event that requires or prolongs in-patient hospitalization
- Any event that results in persistent or significant disability/incapacity
- Any congenital anomaly/birth defect diagnosed in a child of a subject who participated in this study and received investigational drug
- Other medically important events that in the opinion of the investigator may jeopardize the subject or may require intervention to prevent one of the other outcomes listed in the definition above

A new diagnosis of cancer should also be considered serious and should be reported on the Serious Adverse Event (SAE) form. In the case of a death on study, the immediate cause of death should be notified as an SAE.

Overdose and pregnancy are not in and of themselves adverse events or SAEs. However, if there are subsequent adverse events or SAEs as a result of overdose or pregnancy, these events should be captured on the adverse event and SAE forms, as appropriate.

Note: A pre-scheduled or elective procedure or a routinely scheduled treatment shall not be considered an SAE, even if the subject is hospitalized, provided the site stipulates that:

- a) the pre-scheduled elective procedure or routinely scheduled treatment was scheduled prior to obtaining the subject's consent to participate in the clinical trial,
- b) the condition requiring the pre-scheduled elective procedure or routinely scheduled treatment was present before and did not worsen or progress between the subject's consent to participate in the clinical trial and the time of the procedure or treatment, and
- c) the pre-scheduled elective procedure or routinely scheduled treatment is the sole reason for admission and intervention.

However, if complications occur during procedures or surgeries, they are considered to be adverse events and should be recorded. Any adverse event classified as serious must be reported immediately to the CRO via the electronic data capture (EDC) system. \.

In the event of a medical emergency when knowledge of the subject's treatment assignment would influence the subject's clinical care, the principal investigator must contact the Medical Monitor to describe the emergency. Only under these circumstances will unblinding of the

subject's treatment assignment be authorized. Refer to Section 12.4 for emergency decoding procedures.

12.3.1 Immediate Reporting of Serious Events

The study sponsor must immediately be made aware of events classified as SERIOUS in order to adhere to all applicable laws and regulations for reporting serious events. Therefore, it is the investigator's responsibility to ensure the following:

Initial Reports

All SAEs occurring from the time of informed consent until 30 days following the last administration of study drug must be reported to Medpace Clinical Safety **within 24 hours** of the knowledge of the occurrence (this refers to any adverse event that meets any of the aforementioned serious criteria). All serious adverse events that the investigator considers related to study drug occurring after the 30-day follow-up period must be reported to the Sponsor.

To report the SAE, complete the SAE form electronically in the EDC system for the study. When the form is completed, Medpace Safety personnel will be notified electronically and will retrieve the form. If the event meets serious criteria and it is not possible to access the EDC system, send an email to Medpace Safety at [contact] or call the Medpace SAE hotline (phone number listed below), and fax the completed paper SAE form to Medpace (fax number listed below) within 24 hours of awareness. When the EDC system becomes available, the SAE information must be entered within 24 hours of the system becoming available.

Safety Contact Information:

Medpace Clinical Safety

Medpace SAE hotline – USA:

[contact], [name] **or** [contact], [name]

[contact] **or** [contact]

e-mail: [contact]

Follow-Up Reports

The investigator must continue to follow the subject until the SAE has subsided or until the condition becomes chronic in nature, stabilizes (in the case of persistent impairment) or the subject dies.

Within 24 hours of receipt of follow-up information, the investigator must update the SAE form electronically in the EDC system for the study and submit any supporting documentation (e.g., subject discharge summary or autopsy reports) to Medpace Clinical Safety via fax or e-mail. If it is not possible to access the EDC system, refer to the procedures outlined above for initial reporting of SAEs.

The investigator must also notify the local review committee, (ie. Institutional Review Board (IRB) or Ethics Committee (EC) as per local IRB/EC requirements. Documentation of these

reports must be kept in the site's study files and will be checked routinely by the Clinical Monitor.

Any serious event that has onset of informed consent that is unresolved at the time the subject permanently discontinues the study must be followed until the event resolves or until the subject's clinical course has stabilized.

12.3.2 Reporting of Serious Events to Regulatory Agencies

After receipt of a serious adverse event report, TaiwanJ Pharmaceuticals (or CRO) will code and classify the serious adverse event and inform regulatory authorities, as necessary, within the required time frames. TaiwanJ Pharmaceuticals or the CRO will complete written safety reports with the assistance of the investigator and other study site personnel, and will submit the reports to regulatory authorities, as needed.

12.3.3 Guidelines for Determining Relationship Causality of Adverse Events

Not related Any event which does not follow a reasonable temporal sequence from administration of study drug AND that is likely to have been produced by the subject's clinical state or other modes of therapy administered to the subject

Related An event that follows a reasonable temporal sequence from administration of study drug OR that follows a known response pattern to the suspected drug OR that is improved by stopping the drug or reducing the dose but recurs with re-challenge AND that cannot readily be explained by the subject's clinical state or other modes of therapy administered to the subject

12.3.4 Guidelines for Determining Severity of Adverse Events

All adverse events and serious adverse events will be graded according to the NCI CTCAE v3.0. Any event not listed in the CTCAE will be graded as follows:-

Grade 1 Mild Adverse Event: symptom(s) barely noticeable to subject or does not make subject uncomfortable; does not influence performance or functioning; prescription drug not ordinarily needed for relief of symptom(s) but may be given because of personality of subject.

Grade 2 Moderate Adverse Event: symptom(s) of a sufficient severity to make subject uncomfortable; performance of daily activity is influenced; subject is able to continue in study; treatment for symptom(s) may be needed.

Grade 3 Severe Adverse Event: symptom(s) cause severe discomfort; symptoms cause incapacitation or significant impact on subject's daily life; severity may cause cessation of treatment with investigational drug; treatment for symptom(s) may be given and/or subject hospitalized.

Grade 4 Life-Threatening or Disabling Adverse Event: symptom(s) symptoms pose significant risk to life or risk of permanent disability.

Grade 5 Death

12.4 Toxicity Management Guidelines

The toxicity management will be based on DAIDS AE Grading system,

Hepatic toxicity:

ALL patients will have increased liver enzymes at baseline. Liver function tests will be monitored with each visit. For any elevated ALT 5-10.0 X ULN (Grade 3 or 4) on study drug, repeat testing and evaluation will be performed in 1 week. Treatment will be interrupted for drug-related Grade 3 AE until their AE Grade is less than 3. Liver function tests and assessment will be performed weekly to ensure resolution of Grade 3 AE. Study drug may be resumed following confirmation of resolution of Grade 3 AE or if investigator confirms AE is keeping with patient's underlying NASH. The investigator must assess whether or not Grade 3 AE is clinically or not clinically significant in the setting of NASH and in reference to baseline ALT levels. Increases in liver enzymes $> 3 \times$ subject's baseline will prompt retesting and patient examination within 1 week. Increases in liver enzymes $> 5 \times$ subject's baseline will prompt immediate drug discontinuation and withdrawal from study. For non-drug related Grade 3 AE, Investigator will perform further clinical management based on subject's clinical condition and/or other biochemistry results.

DAIDS Grading	Lab Value						INR	Clinical management	
	ALT *		AST		Bilirubin (total)			Non Drug Related	Drug Related
Grade 1	1.25-2.5 x ULN	and/or	1.25-2.5 x ULN	and/or	1.1-1.5 x ULN	and/or	1.2-1.3	Non treatment modification	
Grade 2	2.6-5.0 x ULN	and/or	2.6-5.0 x ULN	and/or	1.6-2.5 x ULN	and/or	1.4-1.5	Non treatment modification	
Grade 3	5.1-10.0 x ULN	and/or	5.1-10.0 x ULN	and/or	2.6-5.0 X ULN	and/or	1.5-2.0	Further clinical management will be judged by Investigator	Treatment interruption may be suggested by Investigator
Grade 4	$> 10.0 \times$ ULN	and/or	$> 10.0 \times$ ULN	and/or	$> 5.0 \times$ ULN	and/or	> 2.0	Treatment termination and withdraw	

* Subjects with elevated ALT > 10.0 ULN will be withdrawn from this study.

Discontinuation of treatment should be considered if:

- ALT or AST $> 10 \times$ ULN
- ALT or AST $> 5 \times$ ULN for more than 2 weeks
- ALT or AST $> 3 \times$ ULN and total bilirubin $> 2 \times$ ULN or INR > 1.5
- ALT or AST $> 3 \times$ ULN with the appearance of fatigue, nausea, vomiting, right upper quadrant abdominal pain, fever, rash or eosinophilia ($> 5\%$).

Other toxicities

For other grade ≥ 3 toxicities, if they are considered drug-related adverse event, treatment discontinuation will be suggested based on investigator's judgment. If they are considered non drug-related AE, further clinical management will be conducted based on Investigator's clinical judgment.

All adverse events occurring during the study and follow-up period should be followed until fully resolution or the event is considered chronic or stable.

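### Protocol 12.4 words the action at two hepatic thresholds as both mandatory and discretionary, and INR drives a discontinuation criterion although no on-treatment blood list includes it

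*Protocol*

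**What the plan says.** Protocol 12.4 states its hepatic rules in four places: running text, a DAIDS-graded table, a table footnote and a list below the table.

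- **Drug-related Grade 3 event.** Text: "Treatment will be interrupted for drug-related Grade 3 AE until their AE Grade is less than 3". Table cell: "Treatment interruption may be suggested by Investigator".
- **ALT above 10xULN.** Grade 4 row: "Treatment termination and withdraw". Footnote: "Subjects with elevated ALT > 10.0 ULN will be withdrawn from this study". The list below has ALT or AST above 10xULN as its first bullet and opens with "Discontinuation of treatment should be considered if". Section 10.4.7 repeats these criteria under a permissive lead-in.
- **INR.** One criterion, given in both 12.4 and 10.4.7, combines ALT or AST above 3xULN with total bilirubin above 2xULN or INR above 1.5. INR is also a column of the grading table, and the columns are joined by and/or.
- **Testing.** Section 12.4 says "Liver function tests will be monitored with each visit" but does not name the tests.
- **Grade labels.** The text reads: "For any elevated ALT 5-10.0 X ULN (Grade 3 or 4) on study drug, repeat testing and evaluation will be performed in 1 week". The table puts ALT 5.1 to 10.0xULN in Grade 3 only. It places an INR of 1.5 in both Grade 2 and Grade 3.

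Neither 12.4 nor 10.4.7 says which ULN applies.

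**The concern.** These rules decide when a subject with possible drug-induced liver injury comes off study drug. All subjects enter with raised liver enzymes, and about 12 sites must apply the rules in the same way. If one line of a section orders a stop and another makes it a matter of judgment, two sites facing the same laboratory result can act differently, each pointing to the protocol.

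The INR gap is of another kind. A criterion that depends on a test can act only if the test is done. If PT/INR is not drawn on treatment, the INR half of the criterion and the INR column of the table have no routine data behind them.

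**Working it through.** The plan gives no figure to reproduce here. The check is a comparison of wording, a count of visits and one inequality.

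**Step 1. Wording side by side (Protocol 12.4 unless stated).**

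| Event | Mandatory wording | Discretionary wording |
|---|---|---|
| Drug-related Grade 3 | Running text: interrupt until below Grade 3 | Table cell: investigator may suggest interruption |
| ALT above 10xULN | Grade 4 row; footnote | List below the table; 10.4.7 lead-in |

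Both thresholds conflict within 12.4 itself. The 10.4.7 lead-in is weaker support, because it also covers pregnancy, for which Protocol 10.5 makes stopping compulsory. Its permissive verb is therefore not decisive.

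**Step 2. Is INR measured on treatment?** Section 10.3.2 lists PT and INR as a separate blood item at screening. The on-treatment lists are:

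| Section | Visits | Number | ALT, AST, total bilirubin | PT/INR |
|---|---|---|---|---|
| 10.4.1 | 2 | 1 | yes | no |
| 10.4.2 | 3, 4, 6, 7 | 4 | yes | no |
| 10.4.3 | 5 | 1 | yes | no |
| 10.4.4 | 8 | 1 | yes | no |

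On-treatment visits: 1 + 4 + 1 + 1 = 7. ALT, AST and total bilirubin are itemised at 7 of 7, and PT/INR at 0 of 7. The schedule tables are not used as evidence, because they have no PT/INR row even for screening. Section 6.3 brings in prothrombin time only in follow-up after withdrawal for ALT above 5 times baseline.

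**Step 3. Who is missed?** Read the criterion as (ALT or AST above 3xULN) and (bilirubin above 2xULN or INR above 1.5). The itemised tests detect the bilirubin route. They miss a subject with ALT or AST above 3xULN, INR above 1.5 and bilirubin not above 2xULN. If INR above 1.5 were meant to qualify alone, that subject would still be missed.

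**Step 4. Does the baseline-multiple rule settle the 10xULN conflict?** For liver enzymes above 5 times baseline, 12.4 is unambiguous: such an increase over the "subject's baseline will prompt immediate drug discontinuation and withdrawal from study". This comes later than 10xULN when

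5 x baseline > 10 x ULN, that is, baseline > 2 x ULN.

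The study laboratory's ULN is not given. Assume 40 U/L, the remission range in Protocol 13.4.1.2. Then 2 x 40 = 80 U/L and 10 x 40 = 400 U/L. The rule fails to cover 10xULN only for baselines above 80 U/L. The entry cap of 250 U/L (250/40 = 6.25xULN) leaves room for such baselines. The rule therefore covers some subjects and not others.

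**The case against.** The best defence is that the protocol can be followed as it stands. A site that takes the stricter action satisfies every statement, and the footnote on ALT above 10xULN is both specific and mandatory, whereas the list is a general lead-in to four criteria. This largely stands. A reader might infer that a site could keep a subject on drug above 10xULN and still comply; it could not, because it would breach the footnote and the Grade 4 row. What remains is that the same page offers softer wording for the same value.

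For Grade 3, discretion is already present in the text. Relatedness is a clinical judgment (12.3.3), and drug may be resumed if the investigator attributes the event to underlying NASH. That is true, but this discretion concerns attribution, clinical significance and restarting. It does not decide whether a drug-related Grade 3 event is interrupted in the first place.

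For INR, the uncovered combination is narrow. Section 12.4 requires repeat testing and evaluation, and 11.2.2 lets sites run any test needed for patient welfare. These points limit the gap without closing it: 11.2.2 is a permission, and liver function tests are not defined to include INR. Escalation of grade 3 results (11.4) and the review board (13.6) are real safeguards, but neither says which action applies.

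**Conclusion.** The point holds and should be corrected. Two hepatic action thresholds in Protocol 12.4 carry both mandatory and discretionary wording, and one discontinuation criterion depends in part on a test itemised at 0 of 7 on-treatment visits. The effect is on patient safety and uniform conduct. No bias between arms follows, and power and alpha do not change.

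Two stronger readings are tempting but not supported.

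- **Taking ULN as 20 U/L (women) and 30 U/L (men).** A reader might then infer that the 5-times-baseline rule fails from exactly the screening minimum upward (2 x 20 = 40, 2 x 30 = 60), or that a woman could enter already past 10xULN (250/20 = 12.5). Those limits define efficacy remission in Protocol 5.2.2, not a toxicity ULN. They are also unlikely because the synopsis describes a stratum of ALT below 2xULN, which the entry minimum of above 40 and above 60 U/L would leave empty. That stratification conflicts with the diabetes stratification elsewhere and may be residual text, but it shows how ULN is used. For safety shift tables, 13.4.3.2 uses central laboratory ranges.
- **Treating the loose grade label as altering the study stopping rule.** Section 6.2 counts hepatic events above Grade 3 but does not name a grading system. Sections 12.3.4 and 13.4.3.1 grade adverse events by CTCAE v3.0, while the 12.4 table is DAIDS. The documents do not show that 6.2 uses the 12.4 grades; that needs stating.

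**What to change.** 1. In the 12.4 list, the Grade 4 row, the footnote and 10.4.7, state that study drug will be permanently discontinued at ALT or AST above 10xULN and that off-drug follow-up continues, as 6.1 and 10.1 already intend. Editing all four places also removes the present mixture of stopping drug and leaving the study. State that ULN means the study laboratory's upper limit.
2. Change the drug-related Grade 3 table cell so that treatment will be interrupted, and keep the resumption rule in the text.
3. Require a reflex PT/INR whenever any on-treatment ALT or AST, scheduled or repeat, exceeds 3xULN. State that the INR grades apply when INR is measured, because the reflex test will not find a raised INR without raised transaminases.
4. Label ALT 5.1 to 10.0xULN as Grade 3 only, start INR Grade 3 above 1.5, and say whether the 6.2 stopping rule uses DAIDS or CTCAE v3.0 grades.

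The wording changes have no statistical cost. The reflex test adds one assay at each flagged scheduled or repeat visit. It is not capped at seven per subject, because the weekly and repeat tests in 6.3 and 12.4 can also trigger it. The total depends on the laboratory's ULN (the trigger would be 3 x 40 = 120 U/L at an assumed ULN of 40) and on on-treatment ALT and AST values, which the documents do not give.

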6.3 Reasons for Subject Withdrawal

Any subject may withdraw his or her consent at any time.

Subjects will be monitored carefully during the study. Any subject who experiences an increase in ALT value greater than 3X baseline during the treatment period will be monitored weekly. If ALT values increase to greater than 5X the baseline ALT will be rechecked within 48 hours and if value remains $>$ 5X baseline, the subject will be withdrawn from the study. The subject will then be followed, and ALT, AST, prothrombin time, and total bilirubin will be monitored every 2 weeks thereafter until the value that led to the subject's discontinuation of therapy has returned to the baseline value (Baseline for prothrombin time and total bilirubin is the value obtained at the screening).

Other reasons for withdrawal from the study may include, but are not limited to the following:

- Subject is in violation of the protocol, defined as refusal or inability to adhere to prescribed dosing and/or follow-up regimen.
- Subject is lost to follow-up.
- Subject experiences a serious or intolerable AE that, in the medical opinion of the principal investigator, warrants discontinuation.
- Subject has laboratory safety assessments that reveal clinically significant worsening from baseline values.
- Subject develops, during the course of the study, symptoms or conditions listed in the exclusion criteria.
- Subject requires a medication that is prohibited by the protocol.
- Investigator or TaiwanJ Pharmaceuticals requests an early discontinuation of the trial for any reason.

The investigator may also withdraw a subject upon the request of TaiwanJ Pharmaceuticals or if TaiwanJ Pharmaceuticals terminates the study. Upon occurrence of a serious or intolerable AE, the principal investigator will confer with TaiwanJ Pharmaceuticals. If a subject is discontinued because of an AE, the event will be followed until it is resolved or until the principal investigator or sub-investigator deems the event to be chronic or the subject to be stable.

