8.1. Subject Inclusion Criteria

Subjects must meet all of the following inclusion criteria to be eligible for enrollment into the study:

1. Age \geq 18 years
2. Provision of written informed consent
3. Biopsy-proven NASH within 12 months prior to randomization as reviewed by central pathologist with:
 - NASH activity score (NAS) of 4 or more
 - 10% or more macrovesicular steatosis
 - cytologic ballooning score of at least 1 point
 - hepatic fibrosis of at least 1 point
 - hematoxylin and eosin (H&E) stained slides and/or paraffin block available for independent assessment
4. ALT $>$ 40 U/L for women and $>$ 60 U/L for men at screening and at least once in the previous 12 months.
5. MRI with $>$ 6% hepatic steatosis
6. HbA1c of \leq 9.0
7. Lipid lowering agents (i.e. statins) and allowable antidiabetic treatment (i.e. metformin or sulfonylurea) must be stable at screening and during the study.
8. Agree to use of effective contraceptive measures if female of child bearing potential.

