8.2. Subject Exclusion Criteria

1. The presence of any of the following will exclude a subject from study enrollment: Any chronic liver disease other than NASH (i.e., drug-induced, viral hepatitis, autoimmune hepatitis, primary biliary cirrhosis, primary sclerosing cholangitis, hemochromatosis, A1AT deficiency, Wilsons disease)
2. Cirrhosis, as assessed clinically or histologically
3. Presence of vascular liver disease
4. BMI \leq 25 kg/m²
5. Excessive alcohol use ($>$ 20 g/day) within the past 2 years

6. AST or ALT > 250 U/L.
7. Type 1 diabetes mellitus
8. Bariatric surgery in the past 5 years.
9. Weight gain or weight loss of > 5% in past 6 months or > 10% change in past 12 months.
10. Contraindication to MRI
11. Inadequate venous access
12. HIV antibody positive, hepatitis B surface antigen positive (HBsAg), or HCV RNA positive.
13. Receiving an elemental diet or parenteral nutrition
14. Chronic pancreatitis or pancreatic insufficiency
15. Any history of complications of cirrhosis (i.e. ascites, hepatic encephalopathy, or portal hypertensive bleeding), even if absent or optimized with medical management at time of screening
16. Concurrent conditions:
 - a) Inflammatory bowel disease
 - b) Unstable angina, myocardial infarction, transient ischemic events, or stroke within 24 weeks of screening
 - c) Ongoing infectious, immune mediated disease within previously 1 years
 - d) Any malignant disease (other than basal cell carcinoma of the skin) within previous 2 years
 - e) Prior solid organ transplant
 - f) Any other concurrent condition which, in the opinion of the investigator, could impact adversely on the subject participating or the interpretation of the study data.
17. Concurrent medications including:
 - a) Anti-NASH therapy(s) initiated after the liver biopsy diagnosing NASH. Anti-NASH therapies include S-adenosyl methionine (SAMe), milk thistle, and vitamin E.
 - b) Antidiabetic mediation which may impact NASH histology initiated after the liver biopsy diagnosing NASH including thiazolidinediones (glitazones), dipeptidyl peptidase 4 inhibitors (gliptins) or glucagon-like peptide 1 analogs.
 - c) Immune modulatory agents including systemic steroids, methotrexate, anti-TNF- α therapies (infliximab, adalimumab, etanercept) or anti-integrin therapy (namixilab).
 - d) UGT2B7 enzyme inhibitors (e.g., diclofenac, fluconazole, medroxyprogesterone acetate, meclofenamic acid)

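### Section 12.4 orders withdrawal when unnamed liver enzymes exceed five times baseline, which does not match the ALT-only rule in Section 6.3 and can contradict the 12.4 grading table

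*Protocol*

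**What the plan says.** Protocol Section 12.4 opens its hepatic toxicity text with the statement "ALL patients will have increased liver enzymes at baseline". It then sets limits as multiples of the subject's own baseline. Above three times, the subject is retested and examined. Above five times, the subject's "baseline will prompt immediate drug discontinuation and withdrawal from study". The trigger is written as *liver enzymes*. No enzyme is named, and no grade, causality or recheck condition is attached.

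The table in the same section works in multiples of ULN and has columns for ALT, AST, total bilirubin and INR. Grade 1 is 1.25–2.5, Grade 2 is 2.6–5.0, Grade 3 is 5.1–10.0 and Grade 4 is above 10.0 times ULN, with the same bands for ALT and AST. The action for Grades 1 and 2 is "Non treatment modification". Grade 3 is left to the investigator if not drug related; if drug related, the investigator may suggest interruption. Grade 4 means termination and withdrawal. GGT has no column.

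Section 6.3 states its rule for ALT alone: "If ALT values increase to greater than 5X the baseline ALT will be rechecked within 48 hours". The subject is withdrawn only if the value stays above the limit. The same section lists as a possible further reason: "Subject has laboratory safety assessments that reveal clinically significant worsening from baseline values".

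Section 8.1 requires screening ALT above 40 U/L in women and above 60 U/L in men. AST has only a ceiling, through the exclusion in Section 8.2 of "AST or ALT > 250 U/L". GGT has no entry limit. All three are measured at the study visits (Sections 10.3 and 10.4).

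**The concern.** A mandatory stopping rule should tell every site the same thing about the same laboratory value. Here the analyte is open in one section and fixed in the other, and the text and the table of 12.4 use different scales (own baseline and ULN) without saying which prevails. Where the scales disagree, one site can withdraw a subject and another can continue treatment, both with support in the protocol.

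Subject safety is the first thing at stake. The second is the rate of AEs leading to discontinuation, one of the primary safety endpoints in Section 13.4.3.1, which could then depend partly on which passage a site follows. The trial plans about 12 sites and 20 subjects per arm, and withdrawn subjects are not replaced (Sections 6.3.2 and 7.1).

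**Working it through.** The plan gives no figure to reproduce. The check is threshold arithmetic.

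**Inputs.** Grade bands and the five-times rule come from 12.4, entry limits from 8.1 and 8.2. The documents do not give the ULN used for grading. Results are therefore in ULN multiples, with assumed ULNs for illustration. The printed bands leave small gaps (2.5 to 2.6 and 5.0 to 5.1); values above 2.5 are treated as Grade 2 and values above 5.0 as Grade 3.

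**Rule on the ULN scale.** Let b = baseline ÷ ULN. The limit is passed when value ÷ ULN > 5b. Values just above the limit are:
- Grade 1 if 1.25 ≤ 5b < 2.5, so 0.25 ≤ b < 0.5;
- Grade 2 if 2.5 ≤ 5b < 5.0, so 0.5 ≤ b < 1.0;
- Grade 3 if 5.0 ≤ 5b < 10.0, so 1.0 ≤ b < 2.0;
- Grade 4 if b ≥ 2.0.

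At b = 1.0 exactly, the value must exceed 5.0 × ULN and has already left Grade 2. The clash with the Grade 1–2 row therefore needs a baseline strictly below ULN. If *increase* means an added rise of more than five times baseline, the value must exceed 6b, and the clash needs b < 5/6 = 0.83.

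**AST.** Limit 5 × baseline, as a multiple of three assumed ULNs:

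| Baseline AST (U/L) | Limit (U/L) | ULN 35 | ULN 40 | ULN 50 |
|---|---|---|---|---|
| 20 | 100 | 2.86 | 2.50 | 2.00 |
| 25 | 125 | 3.57 | 3.13 | 2.50 |
| 30 | 150 | 4.29 | 3.75 | 3.00 |
| 45 | 225 | 6.43 | 5.63 | 4.50 |

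Every cell with baseline below ULN lies below 5.0, in Grade 1 or 2. In the last row this is true only for ULN 50. With no AST floor at entry, such baselines are admissible.

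**GGT.** No grade can be assigned, so there is nothing in the table to set against the trigger.

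**ALT.** At the entry floors the limits are 5 × 40 = 200 U/L (women) and 5 × 60 = 300 U/L (men).

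| ULN women / men (U/L) | Women | Men | Grade just above the limit |
|---|---|---|---|
| 20 / 30 | 10.0 | 10.0 | 4: text and table agree |
| 30 / 40 | 6.67 | 7.50 | 3 |
| 40 / 60 | 5.00 | 5.00 | 3 |
| 55 / 65 | 3.64 | 4.62 | 2 |

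The first row borrows the efficacy normal limits; the others are assumed. In Grade 3 the table leaves room for judgement and the text orders withdrawal. For ALT to fall in Grade 2, the ULN must exceed 40 (women) or 60 (men), or the Day 1 baseline must be below the screening floor. Separately, 6.3 requires a recheck before withdrawal and 12.4 requires immediate discontinuation.

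**The case against.** The best defence is that *liver enzymes* means ALT. Sections 5.1.2 and 5.2.2 gloss the term as serum ALT. The surrounding 12.4 text refers to elevated ALT and baseline ALT levels, and the opening statement fits the ALT entry floor. On that reading 12.4 and 6.3 name the same analyte and the AST case disappears.

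This has weight, but does not settle the matter. The glosses sit in an efficacy objective and endpoint. The 12.4 paragraph writes ALT where it means ALT and then changes to an unqualified plural. Its table and discontinuation bullets include AST. The Grade 3 difference and the recheck conflict also remain for ALT alone.

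A reader might infer stronger claims that the documents do not support:
- That 12.4 withdraws subjects for a rise in any liver enzyme. The text does not say so; the term is undefined.
- That a GGT rise is graded 1–2. It is not graded.
- That 6.3 ignores everything except ALT. Only its numeric rule is limited to ALT; it also allows withdrawal for clinically significant laboratory worsening, as a discretionary reason.
- That a withdrawn subject is lost to the primary analysis. Protocol Sections 6.3.1, 10.1 and 10.4.4 ask for end-of-treatment assessments after early stopping. SAP 6.3.1 keeps every dosed subject in the Full Analysis Set, and SAP 6.9.1 imputes missing MRI values.

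It is also fair that the analyte question matters only when AST or GGT passes five times baseline and ALT does not. The documents give no frequency for that.

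**Conclusion.** The fault is a conflict between written stopping instructions. It has three parts:
1. The 12.4 trigger does not name its enzymes, while the 6.3 rule names ALT only and adds a recheck.
2. If AST is included, every subject with baseline AST below ULN (below 0.83 × ULN on the added-increase reading) can pass the withdrawal limit in a grade that the table marks for no treatment change. If GGT is included, the trigger has no grade.
3. Even on the ALT-only reading, text and table differ when five times baseline falls in Grade 3, that is, for baselines from 1.0 to just under 2.0 × ULN.

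Parts 1 and 3 need no assumption about AST. Part 2 depends on the wider reading. The ULNs in the tables are assumptions, but the thresholds in ULN multiples are not.

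The share of subjects affected cannot be derived and may be small. Each withdrawn subject is 1/20 = 5% of an arm. This is not a 5% loss from the primary analysis: the subject leaves the Per Protocol set, which requires 24 weeks of treatment (SAP 6.3.4). The MRI may fall before Week 24, because Section 10.4.6 provides an End of Treatment Visit on early discontinuation. The subject can also count in the AE-discontinuation endpoint. The passages should be reconciled because the rule bears on safety and the correction is cheap.

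**What to change.** Reconcile Section 6.3, the 12.4 text and the 12.4 table in one step:
- name the same analyte or analytes for the baseline-multiple rules in both sections;
- state which instruction governs when the baseline-multiple text and the ULN-based table differ;
- resolve, in the same edit, whether a recheck precedes withdrawal;
- say which enzyme the statement about raised baseline values refers to.

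The sponsor and medical monitor decide which clinical rule applies; the request is only for one consistent rule. The cost is one clarifying amendment or site letter, with no new tests, staff or patients.
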